#### 5.4.2 HANDLING OF PARTICIPANT WITHDRAWALS OR TERMINATION

**Protocol for Discontinuation and Referral.** If a participant shows emergence of severe mood symptoms or greater than low risk of suicide attempt, the UWRAP protocol for assessing and managing suicide risk will be closely followed, supervised by [name] and [name] (see Appendix for UWRAP). However, if a participant is judged to be at imminent risk of suicide and therefore in need of immediate hospitalization, the participant will be immediately discontinued from participation and hospitalized. Our offices are in close proximity to UNC emergency department, and participants requiring immediate emergency care can easily be transferred there. An immediate follow-up phone call to the participant's mental health provider alerting them to the change in symptoms (see information below regarding consent to provider-researcher communication) will occur immediately. If the participant is taking study medication currently, [name] will immediately be contacted and he will break the blind. If it is revealed that the participant is currently in the placebo condition, he will take no further action. However, if it is revealed that the participant was currently in an active hormone stabilization condition, he will oversee the subject's discontinuation of the exogenous hormone according to his best clinical judgment.

#### 5.5 PREMATURE TERMINATION OR SUSPENSION OF STUDY

At six month intervals, the study biostatistician ([name]) will test whether there are significant differences in the occurrence of moderate, severe, and serious AEs in the placebo vs. the experimental condition with alpha set at .05. These results will be provided to the Data Safety and Monitoring Board (DSMB) along with the summary report of enrollment.

Administration of study agent will be halted when three serious AEs\* determined to be "probably related" (i.e., with new onset during study patches/pills) are observed. The PI will immediately notify the DSMB when this occurs. The DSMB will notify the study sponsor and investigators immediately when the third severe event is reported and enrollment screens will stop accepting new study participants. [name] will again perform an unblinded statistical analysis to further determine whether active study medication (E2/P4) is significantly related to greater risk of AEs relative to placebo. All requested documentation will be provided to the DSMB. The DSMB will convene an ad hoc meeting by teleconference or in writing as soon as possible. The DSMB will provide recommendations for proceeding with the study to the PI and the NIH. The study sponsor will inform all appropriate regulatory agencies of the temporary halt and the disposition of the study.

The DSMB will consider stopping the entire study based on the results of the statistical tests provided by [name]: specifically, if the experimental hormone stabilization condition is associated with greater risk of severe or serious AEs than placebo, and there is evidence (as determined by [name]) that such AEs are causally related to the study drug, the study

will be terminated.

**\*Notable examples of serious adverse events in the present study include development of a venous thromboembolism or suicide attempt.**

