### **JUSTIFICATION OF E2/P4 DOSING AND SCHEDULE**

In collaboration with Drs. [name], [name], and [name], the PI has chosen formulations that are bioidentical to human E2 and P4 and will mimic luteal phase concentrations or E2 and P4.

**General Rationale for Route and Dose of E2 and P4.** We will use Climara® 7 day transdermal E2 patches. Peak levels of E2 with Climara (~45 pg/mL), achieved within 24 hrs., correspond roughly to normative luteal E2 levels. No transdermal P4 is available. Although transdermal synthetic progestins are available, these molecules have a high affinity for androgen and mineralocorticoid receptors, limiting their usefulness for testing our hypotheses. Thus, oral prometrium will be dosed b.i.d. to achieve luteal P4 levels to create more **steady-state levels** and minimize the variability that can occur with the oral route.

**Rationale for Timing and Duration of E2/P4.** Administration for 14 days, starting 7 days after a positive urine test for ovulation, will span the range of time in which natural perimenstrual withdrawal would occur and prevent natural withdrawal, thereby allowing us to determine the effects of natural hormone withdrawal vs. experimentally stabilized hormones across the same perimenstrual time period of the menstrual cycle.

**Compliance checks:** Participants will: **1)** be educated on the importance of replacing their patches every 7 days, with individualized strategies to enhance compliance; **2)** be asked about patch adherence and pill compliance on each daily call; **3)** record date of patch application on calendars, reviewed at lab visits; **4)** bring used and unused patches to visits; **5)** be given extra patches for immediate replacement; and **6)** **Serum Levels of E2 and P4** will be collected at each session to both confirm compliance and that exogenous hormones replicate physiologic luteal phase levels.

**Specific Rational for Route and Dose of Estradiol (E2).** By avoiding the first-pass metabolic effects of oral estrogen, **transdermal E2** creates more stable blood levels and a more physiologic profile of E2 relative to its metabolites estrone and estriol. Transdermal E2 also has a superior safety profile than oral estrogen for thromboembolic and metabolic risk. The use of a 7 day transdermal system provides significantly more

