#### 2) *Effects of the Ovarian Hormone Stabilization Protocol on Mood/Anxiety and Behavior*

**Mood/Anxiety.** As the population being studied in this protocol will have elevated psychiatric symptoms, and as ovarian hormone changes are implicated in depressive symptoms in some women, it is possible that adverse mood reactions may occur (1) during the administration of ovarian hormones in the stabilization condition or (2) naturally during the placebo (natural) perimenstrual withdrawal condition. However, because the hormone manipulation mimics (i.e., stabilizes) the luteal hormone levels that women naturally experience, the study is not expected to pose any greater risk to participants than what they experience in daily life. Furthermore, although withdrawal from exogenous E2/P4 (which will mimic normal late luteal phase hormone withdrawal given that exogenous levels will mirror normal luteal physiologic ranges) could elicit negative mood changes, these would not be expected to be any more severe than those that would otherwise have arisen from normal perimenstrual hormone withdrawal—that is, we will have simply delayed the normal withdrawal process.

**Suicidality.** As detailed above, the population will be recruited to achieve a population of women that is simultaneously: (1) experiencing recent suicidal ideation, yet (2) at acceptably low current risk for

**suicidal crisis/attempt** based on an assessment conducted during a screening visit (see **Experimental Eligibility Table in later section**). Because ovarian hormone changes are implicated in psychiatric symptoms in some women, and because such symptoms may increase suicide risk, it is possible that increases in suicidality may occur (1) during the administration of ovarian hormones in stabilization conditions or (2) naturally during the placebo (natural) perimenstrual withdrawal condition. **However, because the hormone manipulation mimics (i.e., stabilizes) the normal physiologic range of luteal hormone levels that women naturally experience, the study is not expected to expose participants to greater risk for suicidality than what they experience in daily life.**

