**Assessment of Outcomes.** Participants will complete phone measures of symptoms and suicidality starting on the first day of patches/pills and ending 5 days following the last patch/pill (phone symbols in figure above). Three lab sessions will measure mediating constructs using behavioral tasks. In each condition, lab visits will occur on days +7, +14, and +22 following ovulation.

**Primary Windows of Comparison for Hypothesis Testing.** To test whether prevention of E2/P4 withdrawal is associated with mediating behavioral constructs and suicide risk, we will compare tasks and interviews in **LABPL2** with **LABEXP2**.

**Blinding of Participants and Staff.** All study staff performing assessments will remain blinded to condition. The natural within-woman variation in menstrual cycle length from one cycle to another will help maintain the participant blind. Few women have regular 28 day cycles, and between-cycle variation up to 8 days is normal. Demand characteristics regarding the impact of hormonal manipulation will be minimized by informing participants that women vary a great deal in their responses to hormones, and our current evidence does not allow us to predict for certain whether hormones have a positive, negative, or neutral effect on women's symptoms (of note, this is scientifically accurate). Finally, although some women may become unblinded later in the extended hormone phase, work by the mentoring team suggests that pharmacologic delay of menses does not influence the course of perimenstrual mood symptoms.

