**Daily Telephone Symptom Measures (PRIMARY AND SECONDARY ENDPOINTS): Depressive Symptoms and Hopelessness** using the 10-item short form of the CES-D and the Beck Hopelessness Scale, **Anxiety Symptoms** (reflecting Threat Sensitivity) using the 6-item short form of the Patient-Reported Outcome Measurement Information System (PROMIS) Anxiety scale; **Impulsive Symptoms** using a five item version of the UPPS-P Lack of Premeditation (i.e., classic impulsivity) subscale; and **Rejection Sensitivity Symptoms** (reflecting social appraisals) using two items with high item-total correlations from the Social Evaluation subscale of the State Self-Esteem Scale. *Each of these inventories has been extensively validated for the measurement of the target construct.* **Suicidal desire and action capacity** will be measured daily using a shortened version of the SITBI.

**Participant Safety:** Emergent changes in suicidality will be managed using the structured University of Washington Risk Assessment and Management Protocol (UWRAP), a safety protocol recommended by NIMH for RCTs since it allows for the safe study of individuals with suicidality. If imminent risk for suicide emerges and cannot be satisfactorily managed by the UWRAP protocol (as determined by [name]), the protocol for discontinuation will be followed. **However, because the manipulation mimics luteal E2/P4 levels that**

women naturally experience, the hormonal manipulation is not expected to pose greater risk than a normal menstrual cycle—the risk will simply be shifted in the stabilization condition.

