**Follow-Up Timeline:**

**Condition 1 (Follow-Up Visits 1-3):**

- Negative Pregnancy Test Confirmed at Enrollment
- Ovulation Testing
- Positive Ovulation Test #1= Day 0
- Study Followup Visits 1-3 Scheduled for days +7, +14, +22
- Study Followup Visit 1 (Day +7): Assessments, administration of study agent patch A and dispensation of pills (**Condition 1**)
- Study Followup Visit 2 (Day +14): Assessments, replacement of study agent patch A with patch B (**Condition 1**)
- Removal of study patch and end of pills on day +21
- Study Followup Visit 3 (Day +22): Assessments, Pregnancy Test

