#### 7.3.4 FINAL STUDY VISIT

Debriefing visits will be scheduled within 15 days of study completion. In this final visit, a final risk assessment will be conducted and the participant will be referred as appropriate for additional clinical care. This final risk evaluation visit is included in order to reduce the likelihood of emergent risk following withdrawal from exogenous hormones in women who had the placebo-experimental condition order. Participants will not be provided with individualized study results.

---

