### 8.2.2 RELATIONSHIP TO STUDY AGENT

For all AEs, Drs. [name] and [name] will urgently collaborate with appropriate clinical supervisors ([name] for physical/medical events, [name] for behavioral/psychological events) to determine the AE's causality based on temporal relationship and his/her clinical judgment. The degree of certainty about causality will be graded using the categories below.

**Definitely Related** – There is clear evidence to suggest a causal relationship, and other possible contributing factors can be ruled out. The clinical event occurs in a plausible time relationship to drug administration and cannot be explained by concurrent disease or other drugs or chemicals. The response to withdrawal of the drug (dechallenge) should be clinically plausible. The event must be pharmacologically or phenomenologically definitive, with use of a satisfactory rechallenge procedure if necessary.

**Probably Related** – There is evidence to suggest a causal relationship, and the influence of other factors is unlikely. The clinical event occurs within a reasonable time after administration of the drug, is unlikely to be attributed to concurrent disease or other drugs or chemicals, and

follows a clinically reasonable response on withdrawal (dechallenge). Rechallenge information is not required to fulfill this definition.

**Possibly Related** – There is some evidence to suggest a causal relationship (e.g., the event occurred within a reasonable time after administration of the trial medication). However, other factors may have contributed to the event (e.g., the participant's clinical condition, other concomitant events). Although an AE may rate only as "possibly related" soon after discovery, it can be flagged as requiring more information and later be upgraded to "probably related" or "definitely related," as appropriate.

**Unlikely to be related** – A clinical event whose temporal relationship to drug administration makes a causal relationship improbable (e.g., the event did not occur within a reasonable time after administration of the trial medication) and in which other drugs or chemicals or underlying disease provides plausible explanations (e.g., the participant's clinical condition, other concomitant treatments).

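### Section 5.5 limits the three-SAE halt to events starting while patches or pills are in use, which conflicts with 8.2.2, 8.5 and 10.4.7.1 and leaves out the post-agent days

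*Combined protocol and SAP*

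**What the plan says.** The halting rule appears three times: in 5.5, 8.5 and 10.4.7.1. Each stops study agent at the third SAE graded *probably related*, and each names venous thromboembolism and suicide attempt as examples of SAEs. Only 5.5 adds an explanation of the grade, introduced by *i.e.*: "with new onset during study patches/pills".

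Section 8.2.2 grades all AEs for causality. Its *probably related* category has a timing condition, "The clinical event occurs within a reasonable time after administration of the drug". It also requires that concurrent disease or other drugs be an unlikely cause, and that the response when the drug is withdrawn (dechallenge) be clinically reasonable.

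On timing, the follow-up timeline in 7.3.3 gives "Removal of study patch and end of pills on day +21", and 4.1 has the daily calls "ending 5 days following the last patch/pill". On risk after the agent, 2.3.1 says that under active treatment "we will have simply delayed the normal withdrawal process", 4.1 says "the risk will simply be shifted in the stabilization condition", and 7.3.4 justifies the debriefing visit as a way to "reduce the likelihood of emergent risk following withdrawal from exogenous hormones". Section 2.2 says the 14 administration days "will span the range of time in which natural perimenstrual withdrawal would occur".

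**The concern.** A halting rule should count the events that the intervention could plausibly cause, at the time it could cause them. By the protocol's own account, the active condition moves hormone withdrawal from the administration days to the days after the last patch and pill. The 5.5 wording stops counting at that moment.

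Followed literally, three suicide attempts shortly after removal of active hormones would not trip the automatic halt, and neither would a venous thromboembolism that presented after day +21 add to the count. The trigger matters because it sets off fixed steps: agent stops, enrollment screening closes, an unblinded comparison is run, and the DSMB meets ad hoc. Without it, those steps depend on discretion. Sections 8.5 and 10.4.7.1 give the grader a different rule, and nothing expressly says which text prevails.

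**Working it through.** The threshold of three has no stated derivation or design rate, so there is no plan figure to reproduce. The check sets the texts and the calendar side by side.

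**Calendar** (day 0 = positive ovulation test)

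- Agent starts on day +7 and ends on day +21 (7.3.3): 21 − 7 = 14 days, which agrees with the 14 days in 6.1.9.
- Calls end 5 days after the last patch or pill (4.1): 21 + 5 = day +26.
- Post-agent call days: +22 to +26, which is 5 days.

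**Post-agent call days covered by each wording**

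| Wording | Days covered | Of the 5 post-agent call days |
|---|---|---|
| 5.5, onset while patches/pills are in use | +7 to +21 | 0 |
| 10.4.4 *treatment timeframe*, read as agent days | +7 to +21 | 0 |
| 10.4.4, read as the study period in 10.4.1 | +7 to +22 | 1 |
| 10.4.4, read as all call days | +7 to +26 | 5 |

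The third row assumes visits on their nominal days. Suppose instead that the whole course moves with the ±2-day visit window while the +7 to +22 period stays fixed. A start on +5 gives post-agent days +20 to +24, of which 3 are covered. A start on +9 gives +24 to +28, of which none is covered.

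**A post-agent SAE under each statement of the rule**

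- *5.5:* not counted, whatever the clinical judgment on cause.
- *8.5 and 10.4.7.1:* counted if it is graded probably related under 8.2.2.
  - Timing: can be met, because a reasonable time after administration is not limited to agent days.
  - Concurrent disease: hard to meet in women enrolled for suicidal ideation, but equally hard for an event that starts on agent. It is not a post-agent gap.
  - Dechallenge: a poor fit. An event that begins because the drug was withdrawn cannot be tested by its response to that withdrawal. A grader who applies this condition strictly may settle on *possibly related*, which the rule does not count.

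**What still captures a post-agent SAE**

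- SAEs are recorded to 30 days after the last day of participation (8.3).
- Severe AEs go to the IRB and DSMB within 1 week (8.4.1).
- Deaths and immediately life-threatening events go to the sponsor within 24 hours regardless of relatedness (8.4.2).
- Unanticipated problems need only be possibly related (8.1.3) and are reported within 1 week (8.4.3).
- The DSMB may ask for tables of all SAEs and can recommend that procedures be altered or stopped (section 8). Its safety evaluation is six-monthly and also as needed when AEs arise (section 9).

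**The case against.** The best reply is that 8.2.2 governs. It applies to every AE, all three statements of the rule use its grade label, and two of them, including the section devoted to halting rules, carry no extra wording. On that view the 5.5 parenthesis is a drafting slip, perhaps meant only to separate new events from baseline suicidality. This carries weight and narrows the point to a conflict between texts. It does not remove it: *i.e.* defines, 5.5 is an operative section on suspending the study, and the dechallenge condition still sits badly with withdrawal-onset events.

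The protocol also expects post-agent withdrawal to be no worse than natural withdrawal (2.3.1) and does not expect shifts in risk to reach crisis or attempt (5.1). That is fair context, but a halting rule exists for what is not expected.

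Two stronger readings are tempting, and the documents do not support them.

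- *Post-agent attempts would go unseen, or the study could not be stopped for them.* The reporting routes and DSMB powers listed above say otherwise. Termination itself rests on a comparison of severe or serious AEs between conditions plus a causality judgment, not on the count of three.
- *The rule counts attempts on placebo and ignores those after active treatment.* Natural withdrawal does fall within the placebo administration days, so such events pass the 5.5 timing test. But timing alone does not count an event. It must also be determined to be probably related, and 10.6.3 breaks the blind to designated clinicians after an attempt or hospitalization, so a placebo event may well be discounted.

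**Conclusion.** The point holds as an inconsistency in the safety trigger that should be corrected. Under the literal 5.5 wording, onset on any of the 5 post-agent call days, or later, adds nothing to the count of three, and this is the period to which the protocol says active treatment moves withdrawal risk. Under 8.5 and 10.4.7.1 the same event may count, at the grader's judgment. The six-monthly AE comparison closes the gap only if *treatment timeframe* in 10.4.4 includes the post-agent days; on the other two readings it covers 0 or 1 of 5 at nominal visit days.

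These are days covered, not events. The documents give no SAE rate, so neither the number of uncounted SAEs nor any change in the chance of a halt can be estimated. The conclusion assumes that *i.e.* is read as a definition and that the last patch and pill fall on day +21. The DSMB charter, which 8.6 says will define the board's data elements, is not among the documents and might set event windows.

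**What to change.** Delete the parenthesis in 5.5. In 5.5, 8.5 and 10.4.7.1, use one sentence: the halt counts any SAE graded probably or definitely related under 8.2.2, with onset from first dose through a stated post-agent window in each condition. The window should cover at least the 5 post-agent call days, and preferably run to the next condition's first dose or, after the second condition, to the debriefing visit. That visit can fall up to 15 days after completion, so a 5-day window alone could miss events found there. Apply the window to all SAEs and not only to mood and suicidality events, so that a late thromboembolism is also covered.

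In 8.2.2, note that a dechallenge response is not required when onset follows the end of the agent. In 10.4.4, define *treatment timeframe* by the same window. Keep the threshold of three.

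The cost is a short wording amendment. No new data collection is needed, because calls already run 5 days past the agent and SAEs are already recorded to 30 days after participation. The downside is that a halt and DSMB review could come somewhat earlier.

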## 6 STUDY AGENT

### 6.1 STUDY AGENT(S) AND CONTROL DESCRIPTION

#### 6.1.1 ACQUISITION

Both Climara patches (transdermal E2) and Prometrium pills (oral micronized P4) will be acquired through UNC Investigational Drug Services from their respective manufacturers.

IDS will order climara + prometrium, placebo patches have been shipped, donated from [name].

#### 6.1.2 FORMULATION, APPEARANCE, PACKAGING, AND LABELING

Please see attached inserts for information about active Climara patches (transdermal E2) and Prometrium (oral micronized P4). Both transdermal E2 and oral micronized P4 are readily commercially available. Placebo patches and pills (both in stock at UNC IDS) are formulated and designed to be identical in appearance to these agents; all packaging and blinding will be accomplished via UNC Investigational Drug Services.

